feasibility of conducting this project (and future projects) by reducing the time and financial resources required. These procedures also reduce the time commitment required of participants which makes it more likely that participants will enroll in and complete the study. This waiver would not adversely affect the rights and welfare of subjects. Of note, UW Health and the Wisconsin Physical Therapy Practice Act require a signed informed consent form for all patients receiving physical therapy services to be completed at the time of initial evaluation.

During the phone screening, minimal personal and health-related information that is not of a stigmatizing nature will be collected in order to determine if a person is potentially eligible to participate. It is desirable to conduct a telephone screening in order to save potential participants travel and travel-related expenses involved with coming to Madison from a distance for the sole purpose of conducting a screening when their eligibility is uncertain. Conducting a phone screening will also give potential participants an advance opportunity to learn more about this research and ask questions prior to participating in the formal consent process. Potential participants may also opt not to consent to conducting a telephone screening and instead may choose to schedule an appointment to conduct the screening and consent process.

Description of the Altered Consent Process: [name] conducted all screenings and [name] conducted consent meetings with potential participants. When contacting individuals for the telephone screening, [name] asked permission to provide more detailed information about this research. Then, [name] provided a detailed verbal description of what is being consented to prior to requesting oral consent to conduct the telephone screening. This includes informing potential participants that they are consenting to allowing the study team to maintain the confidential personal and health information for up to 10 years for the sole purpose of using it to invite the individual to participate in future research conducted by members of this study team at the UW-Madison. See the telephone script for complete details.

Written Informed Consent: A copy of the informed consent document will be provided to potential participants prior to the informed consent meeting. Copies will either be handed to potential participants, e-mailed, or mailed to participants at their request. The current version of the IRB-approved consent/HIPAA forms will be stored in the Neuromuscular Coordination Laboratory and in ICTR OnCore. The PI is solely responsible for ensuring that the most up-to-date version of the consent form is stored at each location and that all outdated forms are destroyed as soon as a new version is approved by the IRB. All collaborating providers and staff will be instructed that only [name] and [name] are approved to obtain written consent from potential participants. Any patient that is inadvertently consented by anyone else will be required to repeat the consent process with [name] prior to being enrolled in this research. Any such events will be reported to the IRB.

The informed consent meeting will occur prior to the start of the first research visit in a private area within the Neuromuscular Coordination Laboratory. Each potential participant will be given a chance to review the form and consider it in private, without the presence of study staff, prior to being asked if they are ready to consent to participation. Prior to requesting that potential participants complete the consent form, [name] discussed the research in detail and answer any questions that arise. Each consented participant will be reminded that s/he may withdraw from the study at any time, for any reason, without any impact on his/her ongoing care. Consent will be fully documented in ICTR OnCore.

Privacy and Confidentiality:

Telephone Screening: Telephone screenings was conducted by [name] in a private room. [name] verifed that the potential participant is also in a place where they feel comfortable talking at that time.

Scheduling: Scheduling of research appointments was done directly with [name] or the research assistant and visits will not appear in Health Link.

Study Visits: Access to the Neuromuscular Coordination Laboratory is restricted to faculty, staff, and students directly associated with the lab. Thus, contact with persons not directly associated with this study is limited. All performance-related outcomes procedures will be conducted in areas specifically designed for the purposes of collecting these types of data.

Sensitive Information: We are not collecting particularly sensitive or any stigmatizing information about participants. The personal information we collect is only that which is needed to contact the participant, his/her primary care provider, and his/her emergency contact. The health information we collect is only that which is required to verify that the individual meets the inclusion criteria.

Retention of Telephone Screening Data: With oral consent provided by potential participants, we intend to retain the information collected during the telephone screening process in order to use it to offer individuals opportunities to participate in additional research studies that will be conducted by the applicants over the next 10 years. This information will only be available to the study team. This information will be de-identified and stored in ICTR REDCap and ICTR OnCore at the conclusion of the study. Each participant will be assigned a unique code which will be utilized to re-identify the information for possible use in future studies. The identification codes will also be stored in ICTR REDCap and ICTR OnCore. This information is intended for internal use only. If at some point in the future the study team determines that it is appropriate to develop a research registry, we will submit a separate application to the IRB for consideration of such a project.

Patient-reported Outcome Measures: Most patient-reported outcome questionnaires will be completed on-line through a secure connection to ICTR REDCap, otherwise paper will be utilized. Paper forms will not contain any information that would identify the participant other than the unique, study ID number. These data will be transcribed into ICTR REDCap immediately following data collection. Any paper data collection forms will be stored in a locked cabinet located in a secured location in the Neuromuscular Coordination Laboratory, University of Wisconsin-Madison. Digital records in ICTR REDCap and ICTR OnCore are password protected and clearance is associated with specific roles. Participants will be indirectly identified in research records through a unique participant identifier. All data will be coded and the link for coded data will be stored in ICTR REDCap and ICTR OnCore. Paper files will be shredded once data analysis is finalized. All identifiable subject information will remain stored in ICTR REDCap and ICTR OnCore. These files will be removed/deleted 10 years following completion of this research. The study team will consult with [name], [contact], [contact] and [name], [contact], [contact] regarding storage of participant data and will recontact them as needed.

Performance-based Outcome Measures: These data will be collected on the KIINCE device and uploaded to ICTR REDCap for further data management, analysis and storage. The retention policy and procedures are the same as for the patient-reported outcome measures.

Competing Interests:

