Progression of the Training: The level of difficulty for each training trial is related to the 20 different rod tilt angles, as described above. Each round of training begins at difficulty level 1. A staircase method is then used to adapt the level of difficulty based on response accuracy. After two consecutive correct responses, the difficulty increases. After each incorrect response, the difficulty decreases. The highest level of difficulty achieved within a round of training is determined by what the participant achieves within the 15-minute time limit.

Definition of Adherence:

Appropriate adherence to the intervention is defined attendance of at least 4 out of 6 intervention visits and/or completion of 8 rounds of training (~15 minutes each) and/or completing 1,600 individual training trials.

Recruitment and Retention Strategies:

We will publish non-proprietary, study-related information on-line (https://ncl.labs.wisc.edu/) highlighting the ongoing work in the lab. Email will be used for efficient and consistent communication with participants if consent to use email is provided. Participants will receive contacts from the study team with reminders regarding completing the patient-reported outcomes and upcoming study visits. Participants will be offered reimbursement of \$25 per visit. A completion bonus of \$50 will be offered to any participant who completes all study-related requirements. Total possible reimbursement per participant is \$250.

Permitted Additional Treatments:

Participants will be advised to continue taking life sustaining medications and medications prescribed to be taken regularly. Performance of a home exercise program for dizziness and imbalance that was prescribed prior to enrollment is permitted so long as this program is not advanced while the participant is on study.

Prohibited Additional Treatments:

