Verticality Perception Testing (General Information): Time Required: 5 minutes (full test battery). Testing will be conducted in sets of 10 trials while participants are either standing upright or standing while tilted to the left or the right 16°. Once in position, participants will be shown the image of a rod on the screen inside VR the headset. Participants will use a dial on the response box to rotate the rod until it is lined up with the direction of gravity, which they are instructed to think as being the direction an object would fall if they let it drop from their hand to the floor. Once they think the rod is lined up with the direction of gravity, they press the button on the response box to record their response. Participants will be encouraged to try to not second guess themselves and to just rotate the rod to the position they think is upright and press the button. During these tests, the rod will be shown in one of three different test scenes: Subjective Visual Vertical, Rod and Frame, or Rod and Disk. These test scenes will be shown in a predetermined, pseudorandomized order. Every 10 trials, the KIINCE device positions the participant in standing upright or standing while tilted 16° to the left or to the right in the frontal plane. The order of body positions is also predetermined in a pseudorandomized manner. This testing takes about five minutes. These data will be collected at each assessment timepoint.

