Rod and Disk Test (RDT) with the Oculus Rift: The clinometric properties of the traditional RDT have been established(1). The image of an annulus comprised of a pseudorandomized pattern of dots will be presented in the VR headset. The image of a rod is also presented within the central region of the annulus that is black (Figure 5). The entire image is presented in low-contrast, grayscale with low luminance to minimize visual after-effects. This image will be rotated at 30° per second in either a clockwise or counterclockwise direction around the participant's line of sight. An image of a rod will be projected into the central portion of the annulus. A batch of rod angles will be predetermined. The batch has a lower limit of +/- 20° from earth-vertical and an upper limit of +/- 70° from earth-vertical. Researchers will control the initial presentation of the orientation of the rod and participants will use a hand-held device to rotate the rod and then indicate when they believe the rod is oriented to gravitational vertical. This assessment will be completed using an Oculus Rift and without reference to external visual cues. Only binocular testing will be completed. We will conduct a total of about 30 trials (the exact number of trials performed in each position will depend on the pseudorandomization of the test, and the average value for performance in each position will be used in data analysis). The test is conducted pseudorandomly interleaved with the SVV and RFT. We will use the mean of absolute value of the error in rod alignment measured in degrees for each body position tested as the measurement variable for this outcome. The analysis metric will be the difference between pre-test and post-test measurement within subjects and by group.

[figure not shown]

Figure 5: RDT Visual Stimulus

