Multisensory Balance Examination (MBE): Time Required: 20 minutes. This test was developed for this research project. It is designed to assess balance during guiet standing in different sensory conditions. The visual conditions are either 1) eyes open or 2) eyes closed. The visual environment conditions are either 1) blank virtual world, 2) vertical line (Figure 6), 3) static, tilted frame (Figure 7), or rotating annulus (Figure 8). The visual environment is controlled using an Oculus Rift. The surface conditions are either 1) non-compliant or 2) compliant (4-inch-thick medium density T-foam). All trials are performed while standing on a force plate with the feet in a self-selected, comfortable position. Subjects perform one trial (lasting 50 seconds) of each condition. The force plate samples COP and direction of ground reaction force. The frequency-dependent height of the Intersection Point (IP)(38) of the ground reaction force is the main outcome derived from this test. For this research, we will study the characteristics of the IP curvature plot for each test trial (See Boehm, et al. 2019 a complete description of this metric). We will also compare the IP curvature for certain conditions versus others in order to assess the impact of manipulating specific sensory inputs on the behavior of the IP. From each comparison, we will be able to explore the contributions of different senses to IP behavior. We will use the IP curves as the measurement variables for this outcome. The analysis metric will be the difference between pre-test and post-test measurement within subjects and by group.

Figure 6: MBE Stationary Vertical Rod Stimulus

[figure not shown]

Figure 7: MBE Tilted Frame Stimulus

[figure not shown]

Figure 8: MBE Rotating Annulus Stimulus (dot pattern rotates at 30 degrees/second)

Additional Measures:

Functional Gait Assessment (FGA): The FGA (9) consists of 10 gait-related items, each being scored on a ordinal scale from 0-3. Thus, the total possible score on the FGA is 30. Test items include walking, walking with head turns, walking heel-to-toe, and walking with eyes closed. This test will be conducted along a 20-foot path in a designated area with markings on the floor that facilitate appropriate scoring based on gait deviations from a straight path. The psychometric properties of the FGA are described elsewhere (9). The FGA will be conducted in accordance with the methods of the original publication (9).

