We believe that the study team is well-equipped to accomplish data and safety monitoring for these studies for several reasons. First, we believe the study team has the requisite training and experience in this type of research. Second, we do not intend to enroll, high-risk or special/vulnerable populations. Third, survival is not an outcome. Fourth, this research is a Efficacy and of short duration. Fifth, the proposed research involves an investigator held exempted IDE. We are also not under any obligation to use independent monitoring as a condition of sponsorship or funding. Thus, we intend to utilize self-monitoring procedures.

Interim Analysis:

No interim analyses will be performed.

Harms:

Risks: Non-clinical Setting:

Physical Interventions Performed Outside a Clinical Setting: Participants complete tests of orientation and balance while in a supported standing position. The goal of these tests is to align images with gravity. All participants will also undergo sensory re-weighting training. The purpose of this training is to refine the perception of gravity and learn how to orient and balance oneself based more on somatosensory rather than visual input.

Non-clinical Setting: Study visits take place at the UW-Madison Neuromuscular Coordination Laboratory.

Plan for Handling Medical Emergencies: We were to call 9-1-1 in the event of a medical emergency. Drs. [name] and [name] were trained in CPR and one or both will be present for all study visits. [name] will provide general medical oversight for the trial. This is consistent with how medical emergencies are handled at outpatient physical therapy clinics that do not have an advanced practice or physician provider on site.

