Potential Psychosocial Risks: This study includes completing a telephone screening. The questionnaires and assessments used in this study are new but are like those that are common and currently in use in clinical practice. These activities are like and of no greater risk than activities of daily living or that would be encountered during a standard clinical examination. Positioning in the device is a mild version of what is experienced by patients in clinical tilt table or rotational chair testing. The sensory re-weighting training is similar treatment activities currently performed in the clinic in that it involves training of orientation and balance. None of these activities is expected to pose significant psychosocial risks; however, many patients with dizziness and/ falls also have symptoms of anxiety. Therefore, some participants could become anxious during testing and/or training.

Common Risks: Studies show these assessment and treatment techniques are safe, well-tolerated, and associated with relatively mild and infrequent adverse reactions(46-48). However, potential adverse events (AE) include vertigo (dizziness), nausea, vomiting, fear of falling, loss of balance, headache, joint pain, and muscle soreness. Dizziness is often associated with emotional distress, such as with fear of falling. Mild dizziness (self-reported intensity $\leq 3/10$) lasting ≤ 15 minutes is an expected,

temporary reaction; thus, only prolonged dizziness (>15 minutes) and/or severe dizziness (self-reported intensity \geq 7/10) will be reported as an AE. Imbalance is also expected with assessment. If a participant reports a prolonged (> 24 hours) of worsened symptoms, he/she will be advised to contact his/her primary care provider for guidance regarding managing symptoms and/or to discuss if continued participation in this research is advisable. Subjects could experience vasovagal syncope due to being relatively immobile in a standing posture for periods of time.

Serious Risks: Falls or any injury that occurs while performing tests or interventions will be reported as a serious adverse event (SAE).

Minimization of Risks:

The risk of vertigo, nausea, and vomiting will be minimized by:

1) stabilizing the participants in a comfortable harness,

2) limiting duration of exposure to visually provocative stimuli (<~5 s per trial),

3) verbally monitoring participant tolerance and comfort to the intervention,

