4) pausing the study for a rest break or terminating the study if symptoms don't resolve, and

5) allowing the participant to sit down with elevated legs within or outside the device during requested rest periods.

The risk of injury due to loss of balance will be minimized by:

1) recruiting participants that are independently ambulatory in the community,

2) providing physical assistance and handles to aid in negotiating the one 6 inch step up onto the device and the one step forward into position, and

3) placing the participant in a full torso harness attached to an overhead frame that prevents them from moving downward more than a few inches or tipping more than 30 degrees.

The risk of anxiety will be minimized by:

1) providing physical assistance stepping onto the device,

2) reassuring the participant that the safety harness will prevent any possible injury if they were not able to support themselves, and

3) guiding the participant through relaxation techniques as appropriate.

The risk of headache, joint pain, and muscle soreness will be minimized by:

1) ensuring that the participant is comfortable at all times via frequent verbal contact,

2) designing the device to be comfortable for all shapes and sizes of participants,

3) moving the person between postures (vertical, leaned left, leaned right) every 10 trials (~ approximately every 30 seconds), and

4) taking seated rest breaks as needed.

The risk of vasovagal syncope is minimized by:

1) asking about history of vasovagal syncope and excluding participants with frequent history (> 1/month),

2) reminding participants to move their legs every 10 trials,

3) using fan to provide gentle air flow for cooling and fresh air,

4) changing posture every 10 trials, and

5) frequently asking participant if they need a rest break or need to terminate the study.

The general risk of being restrained within a device is minimized by:

1) system design that allows the participant to be fully removed from all harness attachments within 5 seconds.

If patients experience a worsening of their condition during this study, they will be directed to contact their primary care provider for guidance. Participants will also be encouraged to consult with their primary care provider or prescriber in order to address any concerns related to withholding p.r.n. medications.

There is also a blood pressure cuff and water available in the lab. [name] is a physical therapy clinician and is trained in CPR and BLS.

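### The risk section's exposure limit of under about 5 s per trial is true of the rod tests and training but not of the MBE, whose rotating-annulus trials last 50 s

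*Combined protocol and SAP*

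**What the plan says.** Under Harms, the Minimization of Risks section lists measures against vertigo, nausea and vomiting. The second is "limiting duration of exposure to visually provocative stimuli (<~5 s per trial". No test is named and no exception is given.

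The opening of that part of the protocol (Risks: Non-clinical Setting) says that participants undergo both orientation and balance testing, then adds "The goal of these tests is to align images with gravity".

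The MBE entry under Performance-based Outcome Measures describes quiet standing under several visual and surface conditions. It states "Subjects perform one trial (lasting 50 seconds) of each condition". One of the scenes is captioned "MBE Rotating Annulus Stimulus (dot pattern rotates at 30 degrees/second".

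The MBE is item 2 under Primary Outcome(s) in the Administrative Information, and Table 3 schedules it at both pre-tests and both post-tests.

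**The concern.** A stated safety figure is not delivered by one of the primary-outcome tests. Someone who reads only the risk section would conclude that no participant watches a provocative scene for more than a few seconds at a time. In the MBE annulus condition the trial lasts 50 s, and nothing says that the annulus is shown for only part of it.

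This matters most for the 15 participants enrolled because they have visually-induced dizziness, which the Specific Aims describe as provoked by busy or moving visual scenes. The same section says that repeated exposure to such images, as a treatment, often worsens symptoms or leads to early withdrawal. At visit 2 the performance tests come immediately before training, and the protocol does not say what state a participant should be in before going on.

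**Working it through.** **Inputs**
- Stated limit: under about 5 s per trial (Minimization of Risks).
- Verticality battery: "This testing takes about five minutes". The SVV, RFT and RDT entries each give about 30 trials.
- Pace in the risk section: position changes "every 10 trials (~ approximately every 30 seconds".
- Training pace, from Definition of Adherence: "completion of 8 rounds of training (~15 minutes each) and/or completing 1,600 individual training trials". I treat the round count and the trial count as describing the same amount of training.
- MBE: 50 s per trial, annulus at 30 degrees/s, four assessments.
- Rod and Disk Test (RDT): "This image will be rotated at 30° per second", the same speed as in the MBE.

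**Step 1. Where the stated limit holds**
- Rod tests: 3 x 30 = 90 trials; 5 x 60 = 300 s; 300 / 90 = 3.3 s per trial.
- Risk-section pace: 30 / 10 = 3.0 s per trial. At that pace 90 trials take 270 s, or 4.5 minutes, which agrees with the stated five minutes.
- Training: 8 x 15 x 60 = 7,200 s; 7,200 / 1,600 = 4.5 s per trial.

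All three are averages, and all lie under 5 s. The limit is reproduced for these tasks.

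**Step 2. Where it does not hold**
- MBE against the limit: 50 / 5 = 10 times.
- MBE against the average rod-test trial: 50 / 3.33 = 15 times.
- Pattern rotation in one MBE annulus trial: 30 x 50 = 1,500 degrees; 1,500 / 360 = about 4.2 turns.

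**Step 3. Cumulative annulus time**

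The protocol does not say how the MBE scenes, eye conditions and surfaces are crossed. I assume one or two eyes-open annulus trials per MBE (one or both surfaces). Eyes-closed trials give no visual exposure.

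| | Longest unbroken exposure | Per assessment | Over four assessments |
|---|---|---|---|
| MBE annulus | 50 s | (1 to 2) x 50 = 50 to 100 s | 200 to 400 s |
| RDT annulus | about 3.3 s (average trial) | 30 x 3.33 = 100 s | 400 s |

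The MBE departs from the stated figure in unbroken duration. In cumulative time it adds no more than the RDT does.

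**The case against.** The best defence is that the limit was never meant for the MBE. The section opens by giving the tests' goal as aligning images with gravity, and later items refer to leaning left and right every 10 trials. Those describe the rod tests and training, not quiet standing. The arithmetic agrees: the figure matches those tasks closely. On this view the defect is a missing scope phrase, and the 50 s is stated openly elsewhere in the same protocol.

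Much of this stands, and the rod tasks are probably where the figure came from. It does not remove the point, because the opening sentence of the risk text also covers balance testing and nothing limits the figure to the rod tasks. If the limit covers the MBE, the MBE does not meet it. If it does not, the risk section omits the longest continuous moving-pattern exposure that the protocol specifies.

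The second defence is that safeguards already exist: harness, verbal monitoring, pausing or terminating, sitting on request, screening questions to find people prone to adverse events, and adverse-event monitoring at every visit. This also stands. These measures do not shorten a 50 s trial, but they lower the stakes. The contingency plan anticipates poor tolerance of testing, although the guidance it promises concerns modifying the intervention.

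Three stronger readings are tempting, and the documents do not support them:
- That the MBE breaks a safety limit set for it. The text is ambiguous, and the likelier reading is an unscoped sentence.
- That 50 s of this scene is shown to be unsafe, or that participants were not told of it. The documents give no adverse-event rates by exposure duration, and the consent pages are not available to check.
- That the protocol's 7/10 and 3/10 dizziness levels should become stop and resume rules. Both levels come from the rules for adverse-event reporting. A 7/10 stop rule could imply carrying on at 4 to 6, which is weaker than stopping on request, and a rating taken after a trial cannot stop that trial. A fixed 3/10 resume level ignores baseline symptoms and could block primary-outcome trials or visit 2 training in the symptomatic group.

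**Conclusion.** The point holds as a minor correction to the safety text. The limit of under about 5 s per trial is stated without scope but is true only of the verticality tests and training. The MBE annulus scene runs about 10 times longer without a break. That ratio uses stated figures only, and takes the annulus to be visible for the whole trial, since nothing says otherwise. The cumulative comparison rests on the assumed one or two annulus trials per MBE, and on the RDT annulus being visible throughout trials that average 3.3 s.

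No alpha, power or sample-size figure is affected. The analysis is touched only if annulus trials are stopped or skipped, probably more often in the symptomatic group. Those intersection-point curves would then be missing selectively from the healthy-versus-symptomatic comparison (Hypothesis A) and, where the annulus supplies the visual-vestibular conflict, from the pre-post comparison (Hypothesis D).

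**What to change.** 1. In Minimization of Risks, confine the 5 s limit to the verticality tests and training, and state the 50 s MBE annulus exposure beside it. Check that the risk description given to the IRB and to participants agrees.
2. State that the existing verbal monitoring and stopping on request apply during MBE annulus trials. Take a brief symptom rating before testing, and start the next trial, or the visit 2 training, once symptoms have settled to about the participant's own pre-test level. Set no fixed numeric stop or resume threshold.
3. Record each stopped or skipped MBE trial with its reason and report the counts by group, so that the planned missing-data sensitivity analysis can use them. Adverse-event reporting alone would not capture this: dizziness of 4 to 6 out of 10 that settles within 15 minutes falls below the reporting threshold.

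The cost is a few lines of protocol text, one short rating before testing, possible brief waits, and one data field. Trial length, test conditions and sample size stay as they are.
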